4.5 Dose Adjustments, Dose Delays, and Missed Doses

There will be no dose adjustments allowed except for weight changes (\pm 10% from the baseline weight measurement) at visits that require weight measurements. If it is determined that a dose level combination exceeds the MTD, participants tolerating that dose level combination will receive subsequent doses at the next lower dose level combination

During treatment for all dose levels, if there is a dose delay between 1 and 5 days, the procedures at the original scheduled visit should be performed as soon as possible. If the delay is more than 5 days, the visit and dose will be considered missed; the procedures at the next scheduled visit should be performed, and subsequent visits will follow every 2 weeks.

If treatment is delayed for > 35 days for participants on dose levels 1 or -1, or > 42 days for participants on dose levels 2 or -2 (> 56 days for participants on a steroid taper), the participant must be permanently discontinued from study therapy, except as specified in Section 4.7 (Duration of Therapy).

4.6 General Concomitant Medication and Supportive Care Guidelines

4.6.1 Supportive care

All supportive measures consistent with optimal patient care will be given throughout the study.

See Appendix X for supportive care considerations for nivolumab and nivolumab and ipilimumab combination administration.

If the confirmed viral load of a participant is > 1,000, the treating physician is advised to make changes to the ART regimen, preferably after consultation with an HIV specialist. If the participant is not receiving ART at the time of study initiation and his/her viral load becomes detectable during study participation, ART initiation may be recommended, at an HIV specialist's direction for the participant's medical care.

Participants requiring chemotherapy or radiation therapy during the study will be taken off study treatment. Any exceptions must be discussed with the study chair. Palliative (limited-field) radiation therapy is permitted if all of the following criteria are met:

- 1) Repeat imaging demonstrates no new sites of bone metastases.
- 2) The lesion being considered for palliative radiation is not a target lesion.

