3.2 Exclusion Criteria

Participants who do not fulfill the criteria as listed in Section 3.1 above, are ineligible. Additionally, the presence of any of the following conditions will exclude a participant from study enrollment:

- 3.2.1 Participants who have received any other investigational agents within the 4 weeks prior to enrollment. Concurrent radiation therapy is not permitted, except palliative (limited-field) radiation therapy, if all of the following criteria are met:
 - 1) Repeat imaging demonstrates no new sites of bone metastases.
 - 2) The lesion being considered for palliative radiation is not a target lesion.
- 3.2.2 Participants with known brain metastases or leptomeningeal metastases must be excluded unless they qualify for enrollment as described below because of poor prognosis and concerns regarding progressive neurologic dysfunction that would confound the evaluation of neurologic and other AEs. Participants with brain metastases are permitted if metastases have been treated and there is no magnetic resonance imaging (MRI) evidence of progression for at least 4 weeks or more after treatment is complete and within 4 weeks prior to the first dose of nivolumab

administration.

- 3.2.3 History of allergic reactions attributed to compounds of similar chemical or biologic composition to ipilimumab, nivolumab, or other agents used in study, or history of severe hypersensitivity reaction to any monoclonal antibody.

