4.6.3 Prohibited therapies

Participants in this study may use standard vaccines. Participants in this study may not use vaccines for the treatment of cancer for up to one month pre- and post-dosing with ipilimumab. Concomitant systemic or local anti-cancer medications including biologics or radiation therapy treatments are prohibited in this study while receiving ipilimumab and nivolumab.

Where possible, routine vaccination for influenza, pneumococcal pneumonia should be given prior to the start of therapy but may be administered during treatment when clinically indicated. Vaccination should be given when there is enough separation to distinguish any vaccine reactions from drug toxicity. There is no experience using live attenuated vaccination during ipilimumab therapy, so that live vaccine should be used cautiously during treatment.

Concomitant systemic or local anti-cancer medications or treatments are prohibited in this study while receiving ipilimumab treatments.

Participants may not use any of the following therapies during the study:

- Any non-study anti-cancer agent (investigational or non-investigational)
- Any other investigational agents
- Any other CTLA-4 inhibitors or agonists
- CD137 agonists, PD-1 inhibitors
- Immunosuppressive agents, unless indicated to manage study therapy induced irAEs
- Chronic systemic corticosteroids, unless indicated to manage study therapy induced irAEs or chronic GVHD at a stable dose prior to study entry
- Any non-oncology vaccine therapies used for the prevention of infectious diseases (for up to 30 days prior to or after any dose of study drug; however, it is suggested that routine vaccinations, including seasonal influenza, be given at

least 2 weeks prior to study treatment).

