9.2 Evaluation of Response for Participants with Kaposi Sarcoma

Response and progression will be evaluated for participants with KS using the ACTG response criteria for KS. For the purposes of this study, participants should be re-evaluated for response every 4 weeks. See Appendix I for the KS Tumor Assessment schedule. Refer to the AMC KS Tumor Assessment MOP for details regarding tumor assessment and photographic documentation.

Evaluable for Toxicity: All participants will be evaluable for toxicity from the time of their first dose of study drug.

Evaluable for Objective Response: Only those participants who have measurable disease present at baseline and have received study drug will be considered evaluable for response.

Response status will be classified as complete response (CR), partial response (PR), stable disease (SD), or progressive disease (PD).

- 9.2.1 Complete response (CR) is defined as the absence of any detectable residual disease, including tumor-associated edema, persisting for at least 4 weeks. Participants in whom pigmented (brown or tan) macular skin lesions persist after apparent complete response, biopsy of at least one representative lesion is required in order to document the absence of malignant cells. Participants without visceral disease are not required to undergo radiographic measurements. In participants known to have had visceral disease, an assessment at restaging with appropriate endoscopic or radiographic procedures should be made.
- 9.2.2 Partial response (PR) is defined as no new lesions (skin or oral), or new visceral sites of involvement (or the appearance or worsening of tumor-associated edema or effusions); AND
 - A 50% or greater decrease in the number of all previously existing lesions lasting for at least 4 weeks; OR
 - Complete flattening of at least 50% of all previously raised lesions (i.e., 50% of all previously nodular or plaque-like lesion become macules); OR
 - A 50% decrease in the sum of the products of the largest perpendicular diameters of the marker lesions

Note: Participants with residual tumor-associated edema or effusion who otherwise meet the criteria for complete response will be classified as having a partial response.

- 9.2.3 Stable disease (SD) is defined as any response not meeting the criteria for CR, PR, or PD.
- 9.2.4 Progressive disease (PD) is defined as follows:

For participants with ≤ 50 cutaneous lesions

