10.4 Analysis of Secondary Endpoints

10.4.1 Preliminary objective response rates

The proportion of participants achieving ORs (by RECIST criteria or KS response criteria, which includes RECIST for visceral disease, or by RECIL for cHL) and their corresponding 95% confidence intervals (calculated using exact Binomial) will be reported separately for solid tumor and cHL according to treatment (combination therapy and single agent) using response criteria designated in Section 9.0. Participants in the expansion cohort and those treated at any Dose Level in the dose de-escalation cohorts will be included. Disease-specific outcomes will be estimated for histologies with > 5 participants. For participants who fail therapy, the proportion with loco-regional vs. distant progression will be summarized. Descriptive statistics will also be compiled for DOR.

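### Sections 3.2.1 and 4.6.1 permit palliative radiotherapy during treatment that 4.6.3 prohibits, and the non-target condition does not keep irradiated lesions out of the Kaposi sarcoma response count

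*Combined protocol and SAP*

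**What the plan says.** **Radiotherapy on study.** Section 4.6.1 opens with a general rule, "Participants requiring chemotherapy or radiation therapy during the study will be taken off study treatment", and asks that exceptions be discussed with the study chair. It then states that "Palliative (limited-field) radiation therapy is permitted if all of the following criteria are met". The two criteria are repeat imaging without new bone metastases, and "The lesion being considered for palliative radiation is not a target lesion". Section 3.2.1 gives the same exception: "Concurrent radiation therapy is not permitted, except palliative (limited-field) radiation therapy, if all of the following criteria are met". Section 4.6.3 says the opposite: "Concomitant systemic or local anti-cancer medications including biologics or radiation therapy treatments are prohibited in this study while receiving ipilimumab and nivolumab". It adds "Concomitant systemic or local anti-cancer medications or treatments are prohibited in this study while receiving ipilimumab treatments". It contains neither an exception nor a reference back to 4.6.1.

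**KS response.** Section 9.2.2 defines PR as no new lesions, no new visceral sites and no new or worse edema or effusion, plus any one of three findings. The first is "A 50% or greater decrease in the number of all previously existing lesions lasting for at least 4 weeks; OR". The second is complete flattening of at least half of all raised lesions. The third is a 50% fall in the summed products of diameters of the marker lesions. Section 9.2.4 accepts a PR in cutaneous disease as an overall PR if nothing has progressed. Appendix XII sets five marker lesions.

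**Analysis.** Section 10.4.1 reports "The proportion of participants achieving ORs (by RECIST criteria or KS response criteria" and the lymphoma criteria, with exact intervals. Disease-specific estimates are planned for histologies with more than five participants.

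**The concern.** A site with a participant who needs palliative radiotherapy finds it allowed in two places and forbidden in a third. Sites may act differently, and the response data would then be collected under different rules.

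The second issue is the endpoint. Where radiotherapy is given, the one condition that concerns response assessment protects target lesions. That is RECIST vocabulary. Section 9.2 scores skin disease on marker or indicator lesions, and two of the three PR routes draw on every existing or every raised lesion. A non-marker lesion that clears or flattens because it was irradiated is then credited to the study drugs. The objective response rate (ORR) in KS, anal and lung cancer is a secondary objective (Section 1.2.2), estimated in small groups without a control arm.

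The protocol recognises the problem before enrolment: Section 3.1.3 rules out KS lesions whose earlier local radiation would prevent response assessment. Sections 9.1, 9.2 and 10.4.1 have no equivalent for radiation given on study. The note on irradiated areas in 9.1.2 is only about whether a lesion is measurable.

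**Working it through.** **1. The plan's own precision figures (Section 10.2).** Exact (Clopper-Pearson) limits are the 0.025 quantile of Beta(x, n−x+1) and the 0.975 quantile of Beta(x+1, n−x), with x = 0.70n.
- n = 12, x = 8.4: 37.97% to 91.96%. The plan states 38% to 92%.
- n = 24, x = 16.8: 48.05% to 86.79%. The plan states 48% to 87%.

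Both reproduce and neither is disputed.

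**2. The two rules.** Reading 4.6.3 as applying only to the combination does not remove the conflict, because the permission in 4.6.1 is not limited to single-agent participants.

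**3. Count route.** Let N be the number of lesions, with five markers neither irradiated nor changed. If every non-marker lesion clears, the decrease is (N−5)/N.
- N = 9: 4/9 = 44%, not a PR.
- N = 10: 5/10 = 50%, meets the threshold.
- N = 40: 20 lesions must clear.

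Clearance must last at least 4 weeks, with no new lesions, new visceral sites or worse edema or effusion. Above 50 lesions, Appendix XII bases assessment on three representative areas, so this arithmetic does not carry over unchanged.

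**4. Flattening route.** With R raised lesions, R/2 rounded up must flatten. Irradiated non-marker lesions can supply all of these if at least that many raised lesions are non-marker.

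| Raised lesions R | Must flatten | Most raised markers that leave the route open |
|---|---|---|
| 2 | 1 | 1 |
| 4 | 2 | 2 |
| 6 | 3 | 3 |
| 10 | 5 | 5 |

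The 4-week duration is written into the count route only.

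**5. RECIST comparison.** PR needs at least a 30% fall in the summed diameters of target lesions (Section 9.1.4.1). Radiotherapy confined to non-target lesions cannot produce that. At most it could turn a PR into a CR, and both already count as responses.

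**6. Size per affected participant.** The number of KS participants is not given, so the denominators are assumptions.
- KS-specific, n = 6 (the smallest group reported): 1/6 = 16.7 points. 0/6 has exact limits 0% to 45.9%; 1/6 has 0.4% to 64.1%.
- KS-specific, n = 12: 1/12 = 8.3 points. 0/12 has 0% to 26.5%; 1/12 has 0.2% to 38.5%.
- Pooled by treatment: Section 10.4.1 adds dose de-escalation participants. Taking only the six that Section 4.2 requires at an MTD, and all as evaluable, 24 + 6 = 30 gives 1/30 = 3.3 points for single agent. For the combination, the expansion size of 12 (Section 4.1) gives 1/18 = 5.6 points, and the 24 of Section 10.2 gives 1/30 = 3.3.

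**The case against.** The strongest reply is that 3.2.1 and 4.6.1 state a rule and its exception, and 4.6.3 merely repeats the rule without the exception. Section 4.6.1 also has more protection than the target-lesion condition: participants requiring radiation come off treatment, exceptions go to the study chair, the field is limited, and imaging must show no new bone metastases. These conditions fit skin KS poorly, since KS participants have no routine scans. Wide irradiation of KS lesions is therefore unlikely. The KS Tumor Assessment manual, to which 9.2 defers for detail, is not among the documents and may say how treated lesions are scored. Response is not primary, and Section 10.2 calls the estimates preliminary.

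Most of this stands as a limit on size. It does not remove either point. Section 4.6.3 names radiation and has no exception, so a reader must supply one. The limited-field and bone-imaging conditions make the KS case rarer without excluding it, and neither says how an irradiated lesion is scored. Coming off treatment does not end ascertainment either: Section 8.7 schedules KS response assessment after discontinuation, and 9.2 sets no cut-off at radiotherapy.

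**Conclusion.** The contradiction between 3.2.1 and 4.6.1 on one side and 4.6.3 on the other is established from the text. So is the gap in KS scoring: lesions irradiated on study can contribute to a PR and, in limited circumstances, meet it alone. Those circumstances are at least ten lesions with every required non-marker lesion cleared, or at least half of the raised lesions non-marker, irradiated and flattened, with no progression in either case. The effect is 16.7 or 8.3 points per case in a KS-specific ORR at the assumed six or twelve participants, and less in the pooled estimate. Frequency is not given and is probably low. Dose-limiting toxicity and MTD decisions are untouched. The silence on scoring is shown for the protocol, not for the unseen KS manual.

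A reader might infer more, and the documents do not support it:
- That any participant with ten or more lesions is exposed. The number that must clear rises with the total.
- That radiotherapy to a growing non-target lesion would keep a RECIST participant in response. Section 9.1.4.2 says unequivocal progression must reflect overall disease status and not growth of a single lesion, so one such lesion would not normally trigger it.
- That the locoregional versus distant progression summary shifts in a known direction. That depends on which site is irradiated.

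**What to change.** 1. Reconcile 3.2.1, 4.6.1 and 4.6.3 so that a single rule on radiotherapy during treatment applies and the sections refer to each other. Which rule applies is for the sponsor and investigators; this review takes no position.
2. State in 9.2 and 10.4.1 that a lesion irradiated on study leaves both the numerator and the denominator of the KS count, flattening and size response criteria. Dropping it from the numerator alone would bias against response: with five of ten lesions irradiated, all five others would have to clear to reach 5/10, whereas excluding the five from both leaves a threshold of three of five.
3. State that an objective response first documented after on-study radiotherapy counts only if it is met on non-irradiated lesions.
4. Record the date and field of any on-study radiotherapy. Section 4.6.2 limits case report form entries on other treatments to prescription medications, and the documents contain no instruction to capture radiotherapy fields.

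The cost is a few sentences and one short data item. The ORR may come out slightly lower.

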4.6.2 Other medications

Participants MUST receive medically appropriate care and treatment for HIV infection, including antiretroviral medications when clinically indicated. Suspension or modification of an antiretroviral regimen during study participation will be permitted (after 8 weeks from study entry) at the discretion of the physician providing HIV care, provided the change and its rationale are carefully documented.

Recommended prophylaxis for opportunistic infections is listed in Appendix VIII. Participants must be instructed to inform the investigators of the current or planned use or all other medications during the study (including prescription medications, over-the-counter medications, vitamins, and herbal and nutritional supplements). It is the responsibility of the investigator to ensure that details regarding all medications are documented. Only prescription medications will be recorded in the case report forms. Bisphosphonates started prior to screening activities or initiated during the course of the study to control bone pain may be used with caution.

As the study will identify DLTs of this treatment regimen during the initial cycle of therapy, prophylactic growth factor (G-CSF) administration is not recommended. Based on observed toxicities, protocol-specified dose modification guidelines should be followed for subsequent therapy cycles. Management of anemia will be at the discretion of the treating physician. No concurrent investigational agents are permitted.

4.6.3 Prohibited therapies

Participants in this study may use standard vaccines. Participants in this study may not use vaccines for the treatment of cancer for up to one month pre- and post-dosing with ipilimumab. Concomitant systemic or local anti-cancer medications including biologics or radiation therapy treatments are prohibited in this study while receiving ipilimumab and nivolumab.

Where possible, routine vaccination for influenza, pneumococcal pneumonia should be given prior to the start of therapy but may be administered during treatment when clinically indicated. Vaccination should be given when there is enough separation to distinguish any vaccine reactions from drug toxicity. There is no experience using live attenuated vaccination during ipilimumab therapy, so that live vaccine should be used cautiously during treatment.

Concomitant systemic or local anti-cancer medications or treatments are prohibited in this study while receiving ipilimumab treatments.

Participants may not use any of the following therapies during the study:

- Any non-study anti-cancer agent (investigational or non-investigational)
- Any other investigational agents
- Any other CTLA-4 inhibitors or agonists
- CD137 agonists, PD-1 inhibitors
- Immunosuppressive agents, unless indicated to manage study therapy induced irAEs
- Chronic systemic corticosteroids, unless indicated to manage study therapy induced irAEs or chronic GVHD at a stable dose prior to study entry
- Any non-oncology vaccine therapies used for the prevention of infectious diseases (for up to 30 days prior to or after any dose of study drug; however, it is suggested that routine vaccinations, including seasonal influenza, be given at

least 2 weeks prior to study treatment).

4.6.4 Precautions

Combination therapy may result in unexpected toxicity especially in novel combinations with other immune modifying agents. A striking example in macaques is presented in Vaccari, *et al.* 2012.

Please note that while unproven, there is a suggestion that autoimmune events, including hepatitis, may occur more frequently at sites of metastases or prior injury.

Caution is advised when considering treatment with high dose IL-2 in participants who have previously been administered ipilimumab, particularly in participants who experienced ipilimumab-related diarrhea/colitis. Colonoscopy or sigmoidoscopy with biopsy may be advisable prior to IL-2 administration once the participant is no longer receiving ipilimumab.

Participants who have received ipilimumab may potentially develop autoimmune disease with subsequent therapy including the appearance of colitis, hypophysitis, or adrenal insufficiency.

4.7 **Duration of Therapy**

In the absence of treatment delays due to AE(s), treatment may continue 92 weeks of nivolumab (with ipilimumab, if receiving dose level 2 or -2) until one of the following criteria applies:

• The development of progression (confirmed PD by RECIST Criteria or PD by the KS evaluation criteria in Section 9.2 or per Section 9.3, utilizing the consensus RECIL (2017). Participants will remain on study treatment until progression is confirmed,

Pregnancy

- All WOCBP should be instructed to contact the investigator immediately if they suspect they might be pregnant (e.g., missed, or late menstrual period) at any time during study participation. Institutional policy and local regulations should determine the frequency of on study pregnancy tests for WOCBP enrolled in the study.
- o The investigator must immediately notify CTEP in the event of a confirmed pregnancy in a study participant.
- Intercurrent illness that prevents further administration of treatment.
- Unacceptable AE(s) which include the following (see also Section 6.0 and specific algorithms in Appendix X):
 - o Any grade 4 events except as noted below.
 - o Grade 3 drug-related autoimmune or inflammatory events including uveitis, pneumonitis, diarrhea, colitis, neurologic AEs, hypersensitivity reaction, or infusion reaction of any duration requires discontinuation except as noted below:
 - o Any other grade 3 non-skin, drug-related AE lasting >7 days including fatigue.
 - o Any grade 3 or 4 drug-related laboratory abnormality or electrolyte abnormality,

- not associated with underlying organ pathology that does not require treatment except for electrolyte replacements **does not** require treatment discontinuation.
- o Grade 3 or 4 amylase or lipase abnormalities that are not associated with DM, associated liver or gall bladder inflammation clinical manifestations of pancreatitis and which decrease to ≤ Grade 2 within 1 week of onset **may** resume study treatment when resolved.
- Any grade 2 drug-related uveitis or eye pain or blurred vision that does not respond to topical therapy and does not improve to Grade 1 severity within the re-treatment period OR requires systemic treatment.
 - Participants requiring > two dose delays for the same type of event should go off protocol therapy.
 - Any AE, laboratory abnormality, or intercurrent illness, which, in the judgment of the investigator, presents a substantial clinical risk to the participant with continued study drug dosing.
- Any participants who require additional immune suppressive treatment beyond steroids should go off study treatment.
- In participants with HIV-cHL, any participant who requires consolidative therapy with high dose chemotherapy followed by stem cell transplantation will be permitted to go off study therapy.
- Withdrawal of informed consent (participant's decision to withdraw for any reason).
- General or specific changes in the participant's condition, or any clinical AE, laboratory abnormality or intercurrent illness, which, in the opinion of the investigator, indicate that continued treatment with study therapy is not in the best interest of the participant.
- Termination of the study by sponsor.
- Participants treated with systemic steroids, except for a short course of tapered steroids for grade 3 rash and physiologic replacement doses, should be off study.
 - Participants who have been treated with steroids and who do not have an immunologically based event (e.g., infectious pneumonia rather than lymphocytic pneumonitis) may be restarted on treatment if asymptomatic after 2 weeks off all steroids.
 - o Tumor assessments should continue as per protocol even if dosing is interrupted.

4.8 **Duration of Follow-Up**

Participants will be followed for 16 weeks or 112 days (based on five half-lives) after removal from study treatment, or until death, whichever occurs first. Participants removed from study for unacceptable AE(s) will be followed until resolution or stabilization of the AE.

